10.15. Sponsor Responsibility for Expedited Safety Reports

Vascular Insights or designee will notify Investigators of all reportable SAEs. This notification will be in the form of an expedited safety report. Upon receiving such notices, the Investigator must review and retain the notice with other study-related documentation.

The Investigator and Institutional Review Board (IRB)/Ethics Committee (EC) will determine if the informed consent form requires revision. The Investigator should also comply with the IRB/EC procedures for reporting any other safety information.

Suspected serious adverse reactions and other significant safety issues reported from the investigational product development program shall be reported to the relevant competent health authorities in all concerned countries per local regulations (either as expedited safety reports and/or in aggregate reports), by the Sponsor or its designated representative.

For use of central IRB for the study, the Sponsor or its designated representative is responsible for submission (or ensuring the submission) of the expedited safety reports to the appropriate IRB for the study.

For this blinded trial, treatment will be unblinded by the Sponsor as necessary to determine the need for expedited reporting, in accordance with global requirements.

11. PLANNED STATISTICAL METHODS FOR ASSESSMENT OF EFFICACY AND SAFETY

11.1. General Considerations

Continuous variables will be summarized using descriptive statistics, specifically the mean, median, standard deviation, minimum and maximum. Categorical variables will be summarized using frequencies and percentages. All statistical tests will be performed at the 0.05 significance level (p -value ≤ 0.050) unless otherwise indicated.

For efficacy analyses, missing post-treatment data will be imputed using last observation carried forward (LOCF). Missing safety data will not be imputed.

11.2. Analysis Populations

11.2.1. Safety Population

The safety population will include all patients who are treated with ClariVein RES. Patients will be analyzed per the treatment they received.

11.2.2. Modified Intent-to-Treat (MITT) Population

The MITT population will include all randomized and treated patients in the safety population who have baseline and at least one post-treatment assessment for the primary efficacy variable. Patients will be analyzed per their randomized dose of STS.

11.3. Primary Efficacy Endpoint

Improvement in patient reported symptoms at Week 12 post-treatment as compared to Baseline using the weekly average HASTI (Heaviness, Achiness, Swelling, Throbbing, Itching) symptom score from the VEINES-QOL/Sym, an instrument of Varicose Vein Symptom Burden in patients with Superficial Venous.

11.3.1. Secondary Efficacy Endpoint

Elimination of saphenous vein reflux at Week 12 post-treatment as demonstrated by duplex ultrasound.

11.4. Tertiary Endpoints

Assessment of patient improvement as compared to the Baseline assessment using the following scales at post treatment Week 12 on the following Quality of Life or patient improvement assessment:

- Clinical-Etiology-Anatomy-Pathophysiology (CEAP) Classification
- European Quality of Life scale (EQ-5D-5L)
- Revised Venous Clinical Severity Score (rVCSS)
- Wong Baker Visual Analog Pain Scale (VAS)

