The study data will be analyzed and reported based on all patients' data from baseline up to the time when all patients have completed the Week 12 post-treatment follow-up visit or have discontinued from the study. If a patient has discontinued from the study, the Last Observation will be carried forward (LOCF) for analysis.

LIST OF ABBREVIATIONS AND TERMS

List of Abbreviations

Abbreviation	Term
AE	Adverse Event
ASV	Accessory Saphenous Vein
CEAP	Clinical-Etiology-Anatomy-Pathophysiology Classification
DICOM	Digital Imaging and Communications in Medicine
DVT	Deep Venous Thrombosis
EO	Ethylene Oxide
EQ-5D-5L	European Quality of Life - 5 Dimensions
FDA	Food and Drug Administration (United States of America)
GCP	Good Clinical Practice
GSV	Great Saphenous Vein
HASTI	Heaviness, Achiness, Swelling, Throbbing, Itching
IC	Intravascular Coagulation
IRB	Institutional Review Board
MDU	Motor Drive Unit
PASTE	Post-Ablation Superficial Thrombus Extension
PE	Pulmonary Embolism
rVCSS	Revised Venous Clinical Severity Score
SAE	Serious Adverse Event
SFJ	Sapheno-Femoral Junction or Saphenofemoral Junction
SSV	Small Saphenous Vein
STS	Sodium Tetradecyl Sulfate
SVS	Saphenous Vein Segment
TS	Treatment Section
US	United States
VAS	Visual Analog Scale
VEINES-QOL/SYM	Venous Insufficiency Epidemiological and Economic Study-Quality of Life Questionnaire
VI	Vascular Insights, LLC

List of Terms and Definitions

Term	Definition
Adverse Event	An adverse event (AE) is any untoward medical occurrence in a patient or clinical investigation subject administered a study product. The occurrence, which may or may not have a causal relationship with the investigational treatment, may include any clinical or laboratory change that does not commonly occur in that patient and is considered clinically significant.
Baseline	Establishment of patient eligibility for study treatment at least 7 days prior to Treatment visit (Visit 2)
CEAP Classification	The CEAP classification is a method for evaluating venous disease of the leg based on clinical , etiologic , anatomic , and pathophysiologic data.
CRO	Clinical Research Organization, which may be assigned responsibility to perform selected function of the study
Day-of-Treatment	The day on which the single-treatment procedure is performed— the treatment begins and ends on the same day (Visit 3)

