5.1. Inclusion Criteria

An individual must meet **all** the following inclusion criteria to be eligible for this study:

1. Written informed consent
2. Age ≥ 18 years ≤ 80
3. Saphenous vein reflux $> 500\text{ms}$ (0.5s), as measured by duplex ultrasound with patient in the standing position
4. Incompetent saphenous vein with vein diameter ≥ 4 mm and ≤ 12 mm, as measured by duplex ultrasound with patient in the standing position
5. Incompetent saphenous vein with treatable length ≥ 10 cm, as measured by duplex ultrasound with patient in the standing position
6. One or more of the HASTI symptoms related to the target vein: heaviness, achiness, swelling, throbbing and itching.
7. Candidate for endovenous procedure for the treatment of venous insufficiency or superficial venous reflux.
8. CEAP Score: C2 (symptomatic), C3, C4, C5
9. rVCSS ≥ 3

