5.2. Exclusion Criteria

An individual will be ineligible for participation in this study if **any** of the follow criteria are met:

1. CEAP Score: C1, C2 (asymptomatic), C6
2. Second incompetent saphenous vein > 4 mm diameter in either leg
3. Arterial insufficiency demonstrated by a history of peripheral arterial disease (PAD) that would preclude the wearing of compression stockings
4. Absence of a palpable pulse at posterior tibial or dorsalis pedis and an Ankle-Brachial Index (ABI) ≤ 0.6
5. Multi-segmental axial deep venous reflux in at least two contiguous venous segments (e.g., femoral and popliteal) in the ipsilateral extremity
6. Previous surgical or endovenous procedure in the treatment section of the target vein (e.g., surgical, thermal ablation, chemical ablation, etc.)

7. Any major surgery, prolonged hospitalization, or pregnancy within 12 weeks prior to Screening (Visit 1)
8. Participation in an interventional clinical study with any investigational product (drug, biologic, device etc.) within 4 weeks prior to Screening (Visit 1)
9. Unable to:
 - a. walk unassisted; and
 - b. stand as needed for duplex ultrasound measurements of vein at scheduled visits
10. Previous superficial thrombophlebitis of the target saphenous vein with scarring in the treatment section
11. Female patients of childbearing potential with a positive result from a pregnancy test at the Screening (Visit 1), Baseline (Visit 2), or at the Day of Treatment (Visit 3)
12. Known sensitivity or allergic response to:
 - a. sodium tetradecyl sulfate (STS) or any of its ingredients; and
 - b. other products if planned for use on the study patient and there is no available alternative, e.g., local anesthetic; latex stockings, or gloves
13. Known history of anaphylaxis or presence of multiple severe allergies
14. Known high risk of thrombosis, e.g., two or more risk factors including, current use of hormonal contraception, current use of hormone replacement therapy, extended periods of immobility, cancer, obesity, recent trauma
15. Known history of deep vein thrombus (DVT) or pulmonary embolism (PE), known history of acute superficial vein thrombus, known hypercoagulable condition, post thrombotic syndrome
16. Known history of drug or alcohol abuse within 2 years of Screening (Visit 1); and/or current chronic narcotic usage, including for pain (e.g., opioids)

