7. VISIT SCHEDULE AND ASSESSMENTS

7.1. Study Visit Schedule and Assessments

A list of all study assessments is included in [Table 3](#), which indicates with an “X” if the assessment performed at that visit.

The Screening (Visit 1) evaluation should be performed \leq 30 days prior to Treatment (Visit 3). Additional screening will be performed at Baseline (Visit 2), not less than 7 days prior to Treatment (Visit 3).

Study visits, tests and/or procedures should occur on schedule per Table 3. Any exceptions will have to be approved by the sponsor.

Table 3: Visit Schedule and Assessments

Visit	Visit 1	Visit 2	Visit 3	Visit 4	Visit 5	Visit 6
	Screening Period		Treatment Period	Post-Treatment Follow-up Period		
	Screening	Baseline	Treatment	Week 1	Week 6	Week 12
Study Day(s)	-30 to -7	-10 to -7	Day 1	Day 7 (±2 days)	Day 42 (±5 days)	Day 84 (±7 days)
Informed Consent	X					
Inclusion/Exclusion criteria	X					
Medical History	X					
Diagnosis and Extent incompetent saphenous vein	X					
Demographics	X					
Physical Exam	X		X			
Pregnancy test (serum)		X				
Pregnancy test (urine)	X		X			
Height	X					
Weight	X					
Vital signs	X	X	X	X	X	X
Hematological Assessment ^a		X		X	X	X
Intravascular Coagulation Assessment ^{b, c}		X	X	X	X	X
Adverse events	X	Continuous				
Concomitant medications and Non-Drug procedures	X	Continuous				
Ultrasound	X	X	X	X	X	X
CEAP Classification	X					X
rVCSS	X					X
HASTI symptoms – 7-day assessment			X	X	X	X
European Quality of Life scale (EQ-5D-5L)		X	X	X	X	X
VEINES-QOL-SYM		X	X	X	X	X
VAS score		X	X (Procedure only)	X	X	X
ClariVein RES procedure			X			

^a Hematological Assessments include: Hemolysis, hematocrit, reticulocyte count, haptoglobins as described in [Section 8.1](#)

^b Intravascular coagulations include Plasma fibrinogen level, Plasma D-dimer level platelet count, Prothrombin time (PT), Partial thromboplastin time (PTT) as described in [Section 8.1](#).

^c Plasma D-dimer level assessments will be conducted at: Baseline (Visit 2) immediately post Treatment (Visit 3) and at Week 1 follow-up (Visit 4); then, only at subsequent follow-up visits [Week 6 (Visit 5) and Week 12 (Visit 6)] if the D-dimer level is higher than it was at Baseline.

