7.3. Screening (Visit 1)

The study IRB approved informed consent form must be signed and dated before any screening procedures are performed, except for any laboratory tests performed as part of standard of care within the study screening window.

Patients will be evaluated against study inclusion and exclusion criteria. Patients must meet all inclusion and none of the exclusion criteria at Screening to be eligible for the study. For details of assessments, refer to [Table 3](#).

At the Investigational site, prior to ultrasound assessment of the venous system, the patient will be asked to stand or walk for 10-15 minutes.

During Screening visit (Visit 1), the Investigator/Investigational Staff will:

1. Perform all Visit 1 assessments per [Table 3](#)
2. At the end of the Screening Visit, *if the patient fails to be eligible* per the Inclusion/Exclusion criteria, the patient will be considered a screen failure and the reason for failure must be documented in the screening log.

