11.8. Analysis of Other Efficacy Endpoints

The primary analysis for each endpoint will use LOCF methodology for the imputation of missing data.

Continuous endpoints will be summarized using descriptive statistics and will be analyzed using a one-sample t-test to test the null hypothesis that the mean change from baseline equals 0.

The secondary efficacy endpoint, the elimination of saphenous vein reflux at Week 12 post-treatment, will be summarized for both treatments combined using the count and percentage, together with a 95% Wilson (score) confidence interval for the proportion.

To evaluate a dose-response relationship, two analyses will be performed for each endpoint. First, the analyses performed for both treatments combined will be repeated for each treatment group separately. Secondly, for continuous endpoints, an ANCOVA will be performed to compare the change from baseline for STS 1% versus STS 3% with treatment as the class variable and with baseline score as the covariate. For vein closure rate, the treatment difference for STS 1% versus STS 3% for the proportion will be assessed by a chi-square test together with a 95% Wilson (score) confidence interval for the treatment difference.

For each continuous endpoint, the change from baseline to each scheduled visit will be analyzed in the same manner as the Week 12 assessment. Both LOCF and observed cases analyses will be performed.

The correlation between Week 12 efficacy endpoints will be explored using a Spearman correlation coefficient for pairs of quantitative variables, and Kendal's tau for the correlation of the elimination of saphenous vein reflux (yes, no) with quantitative variables.

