rVCSS	
Chronic venous disease (CVD) has benefited from the institution of several assessment instruments designed to clarify elements of the disease process. Among these is the revised Venous Clinical Severity Score (rVCSS), which has proven to be a valuable tool for evaluating changes in condition over time with or without intervention. This revision increased the sensitivity and value of the VCSS in interpreting the language of venous disease.
 
VCSS was originally designed and validated as an objective measure of disease severity in patients with CVD. The recent revision resolved ambiguity in the clinical descriptors and improved clarity and ease of use. The rVCSS consists of 10 items with scores ranging from 0 = Absent to 3 = Severe. The

	rVCSS is calculated by the sum of the scores for the 10 items with a max score of 30.
CEAP	The CEAP classification is a method for evaluating venous disease of the leg based on clinical , etiology , anatomic , and pathophysiologic data.

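### rVCSS is never scored at Visit 2, so its change from Baseline starts from the Screening score that had to pass the entry cut, and the tests against 0 count regression to the mean as improvement

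*Combined protocol and SAP*

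**What the plan says.** Section 11.4 lists CEAP, EQ-5D-5L, rVCSS and the pain VAS as tertiary endpoints: "Assessment of patient improvement as compared to the Baseline assessment using the following scales at post treatment Week 12". The List of Terms and Definitions ties Baseline to Visit 2, at least 7 days before treatment, and Section 7.4 describes Visit 2 as the Baseline visit.

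Table 3 (Section 7.1) schedules EQ-5D-5L, VAS and VEINES-QOL/Sym at Visit 2. CEAP has two marks, at Visit 1 and Visit 6 ("CEAP Classification X X"), and the rVCSS row has the same two. Nothing states which value is the baseline for these two scales.

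Section 5.1 requires an rVCSS of at least 3 for entry and sets the CEAP range as "CEAP Score: C2 (symptomatic), C3, C4, C5". Section 5.2 excludes "CEAP Score: C1, C2 (asymptomatic), C6". Section 7.3 fixes when this is judged: "Patients must meet all inclusion and none of the exclusion criteria at Screening to be eligible for the study". Sections 7.4 and 7.5 recheck eligibility at Visits 2 and 3, with screen failure if it is not met, but neither scale is scheduled again at those visits.

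Under Section 11.8, continuous endpoints "will be analyzed using a one-sample t-test to test the null hypothesis that the mean change from baseline equals 0". This is done for both doses combined and then for each dose. An ANCOVA of 1% versus 3% follows, with the baseline score as covariate. Appendix A gives the scale's range: "rVCSS is calculated by the sum of the scores for the 10 items with a max score of 30".

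**The concern.** A patient enters only if the Screening rVCSS is 3 or more. Some patients reach 3 because that reading happened to be high, and patients whose reading happened to be low are turned away. Among those admitted, the Screening score therefore overstates the underlying level, and a second reading is lower on average even if nothing has changed. The cut has a lower bound only, so for rVCSS this shift is always toward improvement.

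Both arms receive active treatment, and the main test compares the mean change with 0. Nothing in that test separates regression to the mean from benefit. At stake are the statements that rVCSS improved, for the combined group and for each dose. The plan also leaves the rVCSS baseline, and so the ANCOVA covariate, undefined.

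The other tertiary scales and the primary endpoint do not share the problem. EQ-5D-5L and VAS are taken at Visit 2, and the HASTI baseline is a 7-day diary kept before treatment.

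**Working it through.** **The plan's own figure.** Section 11.6 states at least 99% power for the HASTI endpoint (mean change -5.44, SD 3.52, two-sided 0.05) with 50 patients and with 25. The standardised change is 5.44/3.52 = 1.545. By the normal approximation, 1.545 × √50 - 1.96 = 8.97 and 1.545 × √25 - 1.96 = 5.77, so power exceeds 99.99% in both cases. The figure reproduces, but it concerns HASTI. The plan states no figure for rVCSS.

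**Inputs from the documents.** Entry at rVCSS ≥ 3 (5.1), judged at Screening (7.3); scale 0 to 30 (Appendix A); one-sample t-test of change against 0 (11.8); 0.05 level (11.1), taken here as two-sided; n = 50, or 25 per arm (11.6).

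**Assumptions.** Before selection, scores are normal with mean μ of 4 to 8 and SD σ of 2.5 to 3. The correlation ρ between two readings is 0.7 to 0.9. There is no treatment effect. The cut is placed at 2.5, a continuity correction for whole-number scores.

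**Formulas.** With a = (2.5 - μ)/σ and λ = φ(a)/(1 - Φ(a)):
- expected change = -(1 - ρ)σλ
- variance of change = (1 - ρ)²σ²(1 + aλ - λ²) + σ²(1 - ρ²)
- the rejection probability follows from the noncentral t, with noncentrality = mean × √n / SD.

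**Worked case (μ = 4, σ = 2.5, ρ = 0.7).** a = -0.6 and λ = 0.459. Expected change = -0.3 × 2.5 × 0.459 = -0.344. Variance = 0.09 × 6.25 × (1 - 0.2755 - 0.2108) + 6.25 × 0.51 = 0.289 + 3.188 = 3.477, so SD = 1.865. Noncentrality at n = 50 is -0.344 × 7.071/1.865 = -1.31, and the test rejects 24.9% of the time.

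| μ | σ | ρ | Screened out | Spurious change | Rejection, n=50 | Rejection, n=25 |
|---|---|---|---|---|---|---|
| 4 | 3 | 0.7 | 31% | -0.46 | 29.6% | 16.7% |
| 4 | 2.5 | 0.7 | 27% | -0.34 | 24.9% | 14.4% |
| 5 | 3 | 0.8 | 20% | -0.21 | 12.4% | 8.5% |
| 6 | 2.5 | 0.9 | 8% | -0.04 | 5.7% | 5.4% |
| 7 | 2.5 | 0.8 | 4% | -0.04 | 5.4% | 5.2% |
| 8 | 3 | 0.7 | 3% | -0.07 | 5.5% | 5.2% |
| 8 | 2.5 | 0.9 | 1% | -0.01 | 5.0% | 5.0% |

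**Sensitivity.** A separate simulation used scores rounded to whole numbers on 0 to 30, with mean 4 to 8, SD 2 to 3 and reliability 0.6 to 0.9. The change ran from -0.59 to about 0, with rejection of 37% to 5% at n = 50 and 21% to 5% at n = 25. Its middle case (mean 6, SD 3, reliability 0.75) gave -0.18 points and 9%.

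**CEAP.** Entry is cut at both ends. With an assumed SD of 1 class and reliability of 0.75, the simulated shift is -0.17 class if the source population centres on C2, 0.00 midway between C3 and C4, and +0.16 (apparent worsening) on C5.

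**Does a second pre-treatment score cure it?** At μ = 4, σ = 2.5, ρ = 0.7, simulation gives:
- Screening score as baseline: -0.34 points, 25% rejection.
- New score as baseline, not used for entry, with independent error: 0 points, 5%.
- New score as baseline, with the ≥ 3 cut applied to it as well: -0.24 points, 15%. About 70% of the bias remains (0.24/0.34).

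**The case against.** The strongest reply is about size. The documents give no rVCSS distribution. A cut of 3 out of 30 is low, and candidates must also have symptomatic disease of at least C2, a HASTI symptom and suitability for an endovenous procedure. Their typical scores may lie well above 3, and at means of 7 to 8 the false-positive rate is close to 5%. The 25% to 30% figures need a screened mean of 4 and a correlation of 0.7, which implies that 27% to 31% of candidates fail on rVCSS alone. This stands. A reader might take those figures as what the trial will suffer, but they are the adverse corner of an assumed range.

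A second reply is that Baseline is being read too strictly. The definition is "Establishment of patient eligibility for study treatment at least 7 days prior to Treatment visit (Visit 2"), which concerns eligibility rather than an analysis value, and Section 4.2 treats Screening/Baseline as one period. Screening as the rVCSS baseline is indeed the natural inference, since no other pre-treatment value exists. That would settle the label, but it leaves change measured from the selected score.

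A reader might also infer that CEAP has a built-in improvement. The documents do not support this. Entry excludes C6 as well as C1 and asymptomatic C2, so the direction is not fixed. Nor do the documents establish that the t-test, planned for continuous endpoints, is applied to a classification. Likewise, sites might be suspected of scoring upward at the threshold, but nothing in the documents bears on that, and it is not part of this point.

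Finally, these are tertiary scales in a 50-patient pilot, and an uncontrolled test against 0 limits any claim of improvement whatever the baseline. Both statements are true. They lower the weight of the point but do not remove this particular, avoidable bias.

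**Conclusion.** The point holds for rVCSS. Its only pre-treatment score is the one used for entry, and the one-sample tests against 0, combined and by dose, count regression to the mean as improvement. The direction follows from the one-sided cut; the size does not follow from the documents. Under the stated assumptions (means 4 to 8, SD 2.5 to 3, correlation 0.7 to 0.9, no treatment effect), the spurious fall is about 0.01 to 0.46 points on a 30-point scale. The false-positive rate is about 5% to 30% at n=50 and 5% to 17% at n=25. It matters only if many candidates score near 3 and the score is not very repeatable.

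For CEAP, only the missing Visit 2 value and the unnamed baseline are established. It would be wrong to extend the point to the dose comparison: both randomised arms passed the same cut, so the ANCOVA is not biased by it. The primary and secondary endpoints are unaffected. This is a cheap improvement to a tertiary analysis, not a threat to the trial's main conclusion.

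**What to change.** - Table 3: add rVCSS and CEAP at Visit 2, or at Visit 3 before treatment.
- Sections 11.4 and 11.8: name that value as the baseline for change and as the ANCOVA covariate.
- Sections 7.4 and 7.5: state that the rVCSS entry criterion is judged on the Visit 1 score only and that the new score is not used for eligibility. Without this, the existing rechecks could apply the cut to the new score and retain most of the bias.

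The bias falls to zero only if errors in the two pre-treatment scores are independent. The Visit 1 and Visit 2 windows overlap (Days -30 to -7 and -10 to -7), so the new score should be made afresh rather than copied forward.

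The cost is a few minutes of scoring at a visit already held, one eCRF page and a few lines of text. The reported rVCSS improvement may be slightly smaller. The change must precede enrolment, because a pre-treatment score cannot be recovered later. If it cannot be made, the minimum is to name Screening as the baseline for these two scales and report within-group rVCSS change descriptively, with this caveat.
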